mRNA	messenger ribonucleic acid
NH	Northern Hemisphere
NIMP	noninvestigational medicinal product
NP	nasopharyngeal
POCBP	person of childbearing potential
PONCBP	person of nonchildbearing potential
PP	per protocol
RSV	respiratory syncytial virus
SAE	serious adverse event
SAP	statistical analysis plan
SARS-CoV-2	severe acute respiratory syndrome coronavirus 2
SC	safety call
SoA	Schedule of Assessments
ULOQ	upper limit of quantification
USV	unscheduled visit
UTR	untranslated region
WHO	World Health Organization

1. PROTOCOL SUMMARY

1.1. Protocol Synopsis

Protocol Title:

A Phase 2, randomized, active-controlled, observer-blind, dose-ranging study to evaluate the safety, reactogenicity, and immunogenicity of mRNA vaccine candidate variations in healthy adults 18 to 49 years of age.

Brief Title:

Study to evaluate the safety, reactogenicity, and immunogenicity of mRNA vaccine candidate variations in healthy adults 18 to 49 years of age.

Regulatory Agency Identifier Number:

Registry	ID
FDA	IND 028259

Rationale:

The aim of this Phase 2 study is to identify common or unique adaptive and innate immune signals or inflammatory biomarkers with predictive value for mRNA vaccine-induced immunogenicity and/or reactogenicity to support the Sponsor's mRNA-based vaccine platform and mRNA-1010 vaccine development. This study will be performed in an exploratory manner

[figure not shown]
CCI
[Redacted text block]

Objectives and Endpoints:

Objectives	Endpoints
Primary	

To evaluate the safety and reactogenicity of mRNA-1010 vaccine candidate variations.	
Solicited local and systemic ARs through 7 days after study intervention.Unsolicited AEs through 28 days after study intervention.Medically attended AEs from Day 1 to EoS.AESIs from Day 1 to EoS.SAEs from Day 1 to EoS.AEs leading to study or treatment discontinuation from Day 1 to EoS.

Objectives	Endpoints
Secondary	

To evaluate the humoral immunogenicity of mRNA-1010 vaccine candidate variations at evaluable humoral immunogenicity timepoints.	
GMT at indicated timepoints as measured by HAI assay.GMFR, comparing each timepoint with D1 (Baseline) as measured by HAI assay.Percentage of participants with seroresponse for mRNA-1010 at indicated timepoints, as measured by HAI assay.

CCI

Abbreviations: AE=adverse event; AESI=adverse events of special interest; AR=adverse reaction; D=day; EoS=end-of-study; GMFR=geometric mean fold rise; GMT=geometric mean titer; HAI=hemagglutination inhibition; LLOQ=lower limit of quantification; SAE=serious adverse event.

^a Vaccine seroresponse is defined as an increase of antibody titers and concentrations from predose below the LLOQ to $\geq 4 \times$ LLOQ, or at least a 4-fold rise if predose is \geq LLOQ.

Overall Design Synopsis:

This will be a randomized, observer-blind, Phase 2 study to evaluate the safety, reactogenicity and immunogenicity of mRNA-1010 vaccine candidate variations using a systems biology approach in healthy adults 18 to 49 years of age.

Approximately 270 participants will be randomly assigned in a ratio of 2:1:2:1:1:2 to one of 6 study arms to receive one of the following treatments:

- mRNA-1010 at 1 dose level CCI administered as a single dose.
- mRNA-1010.4 at 1 of 2 dose levels CCI administered as a single dose.
- mRNA-1010.6 at 1 of 3 dose levels CCI administered as a single dose.

CCI

Enrollment in the study arms will proceed in parallel.

Except for appropriately delegated unblinded pharmacists, vaccine administrators, and monitors, all personnel involved in the conduct of the study will remain blinded to individual treatment assignment until planned study unblinding or EoS.

Safety monitoring for this study will include the blinded study team members, including, at least, the Sponsor Medical Monitor, a CRO Medical Monitor, and an unblinded IST. The unblinded IST will comprise 3 members who are not directly involved in the conduct of this study. The

study team will conduct ongoing blinded safety reviews during the study and will be responsible for notifying the unblinded IST in case of potential safety signal events. Details regarding composition, responsibilities, and procedures of the IST will be presented in the IST charter.

An independent CEAC of medically qualified personnel, including cardiologists, will review all suspected cases of myocarditis and pericarditis to determine if they meet CDC criteria of “probable” or “confirmed” events which are reported in ongoing interventional clinical trials per the CEAC charter.

Brief Summary:

The study aims to identify common or unique adaptive and innate immune signals or inflammatory biomarkers with predictive value for immunogenicity and/or reactogenicity of mRNA-1010, mRNA-1010.4 and mRNA-1010.6 in healthy adult participants 18 to 49 years of age.

Study details include:

- Study visits for all participants will consist of a Screening Visit (up to 28 days before the D1 visit), a Study Intervention Visit at D1, and Clinic Visits **CCI** [REDACTED]
- All participants will be asked to complete an eDiary for solicited ARs for 7 days (ie, the day of study intervention dosing and 6 subsequent days).
- Frequent blood samples will be collected for the first 7 days to support the exploratory objective of the study.
- Collection of all AEs will be through 28 days after study intervention dosing (ie, the day of study intervention dosing and 27 subsequent days). Collection of MAAEs, AESI, SAEs, and AEs leading to discontinuation from study participation will continue through **CCI** [REDACTED]/EoS.

Number of Participants:

Approximately 270 participants will be enrolled.

Note: *Enrolled* means participants’ or their legally acceptable representatives’, agreement to participate in a clinical study following completion of the informed consent process and screening. Potential participants who are screened for the purpose of determining eligibility for the study, but do not participate in the study, are not considered enrolled, unless otherwise specified by the protocol. A participant will be considered enrolled if the informed consent is not withdrawn prior to participating in any study activity after screening.

Study Arms and Duration:

- The study will comprise 6 study arms.
- The total duration of study participation is up to 7 months from the Screening Visit.

1.2. Schema

Not Applicable.

1.3. Schedule of Activities

The SoA is listed in [Table 1](#).

Table 1: Schedule of Activities

Visit Number		1	2	3	4	5	6	7	8	9	10	USV ^a	
Type of Visit	C	C	C	C	C	C	SC	C	SC	SC	C	C	
Month Timepoint		CCI											
Study Visit Day	Screening ^b	CCI											
Window Allowance (Days)	-28	NA	NA	0	±1	-1 to +3	-7 to +3	±5	±5	±5	±5	±14	NA
Days from Last Study Intervention		CCI											
ICF, demographics, concomitant medications, medical history	X	X											
Inclusion/exclusion criteria	X	X											
Physical examination ^d	X	X											
Vital signs ^e	X	X											
Pregnancy testing ^f	X	X											
Blood for humoral immunogenicity ^g		X				X	X		X			X	

Visit Number		1	2	3	4	5	6	7	8	9	10	USV ^a	
Type of Visit	C	C	C	C	C	C	C	SC	C	SC	SC	C	C
Month Timepoint		CCI											
Study Visit Day	Screening ^b	CCI											
Window Allowance (Days)	-28	NA	NA	0	±1	-1 to +3	-7 to +3	±5	±5	±5	±5	±14	NA
Days from Last Study Intervention		CCI											
NP swab for virus detection ^h		X											X
Randomization		X											
Study intervention (including 30-minute postdosing observation period)		X											
eDiary activation for recording solicited ARs (7 days) ⁱ		X											

Visit Number		1	2	3	4	5	6	7	8	9	10	USV ^a	
Type of Visit	C	C	C	C	C	C	C	SC	C	SC	SC	C	C
Month Timepoint		CCI											
Study Visit Day	Screening ^b	CCI											
Window Allowance (Days)	-28	NA	NA	0	±1	-1 to +3	-7 to +3	±5	±5	±5	±5	±14	NA
Days from Last Study Intervention		CCI											
Review of eDiary ARs ^j						X							
Follow-up safety calls ^k								X		X	X		
Unsolicited AEs ^l		X	X	X	X	X	X						
SAEs	X	X	X	X	X	X	X	X	X	X	X	X	X
AESIs, MAAEs, and AEs leading to withdrawal from the study ^m		X	X	X	X	X	X	X	X	X	X	X	X
Concomitant medications and nonstudy vaccinations ^m		X	X	X	X	X	X	X	X	X	X	X	X

Abbreviations: AE=adverse event; AESI=adverse event of special interest; AR=adverse reaction; BMI=body mass index; C=clinic; COVID-19=coronavirus disease 2019; D=Day; EoS=end-of-study; eDiary=electronic diary; FDA=Food and Drug Administration; FSH=follicle-stimulating hormone; ICF=informed consent form; M=month; MAAE=medically attended AE; NA=not applicable; NP=nasopharyngeal; SAE=serious adverse event; SC=safety call; USV=unscheduled visit.

Note: In accordance with “FDA Guidance on Conduct of Clinical Trials of Medical Products during COVID-19 Public Health Emergency”(DHHS 2020),
Investigators may convert study site visits to telemedicine visits with the approval of the Sponsor.

- a. Participants may experience AEs that necessitate a USV. Additional examinations may be conducted at these visits as necessary to ensure the safety and well-being of participants during the study.
- b. The Screening Visit and Day 1 may be performed on the same day or a different day. Additionally, the Screening Visit may be performed over multiple visits if within the 28-day screening window. If a participant returns for the D1 visit more than 28 days after their Screening Visit for any reason and continues to provide consent to participate in the study, the participant may be rescreened, for study eligibility. All assessments for eligibility must be repeated.
- c. A blood draw will be collected at 6 hours post vaccine injection on D1.
- d. A full physical examination, including height, weight, and BMI will be performed at Screening. Symptom-directed physical examinations may be performed at other timepoints at discretion of the Investigator. On each dosing day before injection, the arm receiving the injection should be examined and the associated lymph nodes should be evaluated. Any clinically significant finding identified by a healthcare professional during study visits should be reported as an MAAE.
- e. Vital signs measurements: Systolic and diastolic blood pressures, pulse rate, respiratory rate, and body temperature. The preferred route of temperature assessment is oral. On the day of vaccination, vital signs will be collected once before vaccination and once at least 30 minutes after vaccination. Vital signs may be collected at other clinic visits in conjunction with a symptom-directed physical examination.
- f. A pregnancy test either via blood or point-of-care urine test will be performed at the Screening Visit and before the vaccine dose on Day 1, if Day 1 is not on the same day as the Screening Visit. At the discretion of the Investigator, a pregnancy test either via blood or point-of-care urine can be performed at any time. If a urine test cannot be confirmed as negative (eg, an ambiguous result), a serum pregnancy test is required. The participant’s FSH level may be measured at the Screening Visit, as necessary, and at the discretion of the Investigator, to confirm postmenopausal status.
- g. D1 (Baseline) blood samples for **CCI** [REDACTED]
- h. An NP swab specimen for viral respiratory pathogens will be collected prior to the study intervention administration on Day 1. At USVs participants with symptoms of respiratory tract infection may be tested by NP swab for respiratory viruses at the Investigator’s discretion to include influenza, RSV and SARS-CoV-2, which may impact analyses of reactogenicity and immunogenicity.
- i. eDiary entries will be recorded by the participant at approximately 30 minutes after vaccination while at the clinic with instruction provided by study staff. Study participants will continue to record in the eDiary each day, preferably in the evening and at the same time each day, on the day of vaccination and for 6 days following vaccination. Any solicited AR that is ongoing beyond Day 7 will be reported until resolution.
- j. Solicited ARs recorded in the eDiaries that is ongoing beyond 7 days after injection will be followed up by the study site staff at the next scheduled telephone call or at the next study site visit. Any medication recorded in eDiaries that is taken to prevent or treat pain or fever will also be reviewed at this time.
- k. Trained study personnel will call all participants to collect information relating to any MAAEs, AESIs, AEs leading to withdrawal from the study, SAEs, information on concomitant medications associated with those events; receipt of any nonstudy vaccinations; and receipt of any systemic steroids, immunosuppressive therapies (drugs or biologics), immunoglobulins, and/or blood products.
- l. All unsolicited AEs will be recorded starting the day of each study intervention, and through 28 days following each study intervention.
- m. All concomitant medications will be recorded through 28 days after vaccination. All concomitant medications relevant to or for the treatment of the SAE, AESI, MAAE, or AE leading to study withdrawal will be recorded from D1 through EoS. Any nonstudy vaccinations will be recorded from D1 through EoS.

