8.4.1. Time Period and Frequency for Collecting AE and SAE Information

All SAEs will be collected from the signing of ICF until the last day of study participation at the timepoints specified in the SoA ([Table 1](#)).

All, AESIs, MAAEs, and AEs leading to withdrawal from the study will be collected from the start of study intervention until the last day of study participation at the timepoints specified in the SoA ([Table 1](#)).

All other (unsolicited) AEs will be collected from the time of the administration of study vaccination through 28 days (the day of study vaccination and the subsequent 27 days) (see the SoA [[Table 1](#)]).

Solicited ARs will be collected during the solicited period, for 7 days (the day of study vaccination and the subsequent 6 days).

Non-serious medical occurrences that begin before the start of study intervention but after obtaining informed consent will be recorded as medical history/current medical conditions, not as AEs; however, if the condition worsens at any time during the study, it will be recorded and reported as an AE.

All SAEs will be recorded and reported to the Sponsor or designee immediately and under no circumstance should this exceed 24 hours, as indicated in [Section 10.3.5](#). The Investigator will submit any updated SAE data to the Sponsor within 24 hours of it being available.

Investigators are not obligated to actively seek information on AEs or SAEs after conclusion of the study participation. However, if the Investigator learns of any SAE at any time after a participant has been discharged from the study, and the Investigator considers the event to be

reasonably related to the study intervention or study participation, the Investigator must promptly notify the Sponsor.

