8.4.7. Medically Attended Adverse Events

A MAAE is an AE that leads to an unplanned visit to a healthcare practitioner. This would include visits to a study site for unscheduled assessments (eg, rash assessment, abnormal laboratory follow-up) and visits to healthcare practitioners external to the study site (eg, emergency room, urgent care, primary care physician). Investigators will review unsolicited AEs for the occurrence of any MAAEs.

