10.3.3. Definition of MAAE

A MAAE is an AE that leads to a USV to a healthcare practitioner. This would include visits to a study site for unscheduled assessments not required per protocol (eg, rash assessment, abnormal laboratory follow-up) and visits to healthcare practitioners external to the study site (eg, emergency room, urgent care, primary care physician).

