## 3. Study Endpoints

### 3.1. Primary Endpoints

The primary objective will be evaluated by the following endpoints:

- Solicited local and systemic adverse reactions (ARs) through 7 days after study intervention.
- Unsolicited adverse events (AEs) through 28 days after study intervention.
- Medically attended AEs (MAAEs) from Day 1 to end of study (EoS).
- Adverse events of special interest (AESIs) from Day 1 to EoS.
- Serious adverse events (SAEs) from Day 1 to EoS.
- AEs leading to study or treatment discontinuation from Day 1 to EoS.

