### 6.3.1. Adverse Events

An AE is defined as any untoward medical occurrence associated with the use of a drug in humans whether it is considered drug related or not. Summaries and analyses of AE newly occurred after study vaccination or any AE already present that worsens after exposure to study vaccination will be provided. Adverse events will also be evaluated by the investigator for the coexistence of MAAE which is defined as an AE that leads to an unscheduled visit to a healthcare practitioner.

Unsolicited AEs will be collected for up to 28 days after injection; SAEs, MAAEs, AESIs, and AEs leading to discontinuation of study participation will be collected throughout the study.

Unsolicited AEs will be coded by PT and SOC using MedDRA and summarized by treatment group. Separate summaries will be provided for unsolicited AEs up to 28 days after injection and similarly for those throughout the study, unless otherwise specified.

All summary tables (except for the overall summary of AEs) for unsolicited AEs newly occurred after study vaccination or already present that worsens after exposure to study vaccination will be presented by SOC and PT with counts of participants included. SOC will be displayed in internationally agreed order ([Appendix F](#)). PT will be displayed in descending frequency in the overall group and then alphabetically within SOC. When summarizing the number and percentage of participants with an event, participants with

multiple occurrences of the same AE or a continuing AE will be counted once. Participants will be presented according to the highest severity (the strongest relationship) in the summaries by severity (of related AEs), if participants reported multiple events under the same SOC and/or PT.

Percentages will be based upon the number of participants in the Safety Set within each treatment group.

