### 6.3.1.2. AEs by System Organ Class and Preferred Term

The following summary tables of AE newly occurred after study vaccination or any AE already present that worsens after exposure to study vaccination will be provided by MedDRA SOC and PT using frequency, counts, and percentages (i.e., number and percentage of participants with an event):

- All unsolicited AEs up to 28 days after injection
- All unsolicited treatment-related AEs up to 28 days after injection and up to EoS throughout the study
- All unsolicited AE up to 28 Days After Injection with Occurrence in  $\geq 1\%$  of Participants in Any Vaccination Group
- All serious AEs up to 28 days after injection and up to EoS throughout the study
- All serious AEs that are treatment-related up to 28 days after injection and up to EoS throughout the study
- All unsolicited AEs leading to discontinuation from participation in the study up to 28 days after injection and up to EoS throughout the study
- All unsolicited severe AEs up to 28 days after injection
- All unsolicited severe AEs that are treatment-related up to 28 days after injection
- All unsolicited medically attended AEs up to 28 days after injection and up to EoS throughout the study
- All unsolicited medically attended AEs that are treatment-related up to 28 days after injection and up to EoS throughout the study
- All AESIs up to 28 days after injection and up to EoS throughout the study
- All non-serious AEs up to 28 days after injection
- All non-serious severe AEs up to 28 days after injection

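### Post-injection findings at scheduled visits are MAAEs under schedule footnote d but not under the MAAE definition, so sites can count a primary endpoint differently

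*Protocol*

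**What the plan says.** **The broad rule.** Footnote d in Protocol Section 1.3 reads: "Any clinically significant finding identified by a healthcare professional during study visits should be reported as an MAAE". SAP Appendix E carries the same sentence. The footnote hangs on the physical examination row, which is marked at Screening and Day 1. Its text, however, speaks of study visits in general and also covers symptom-directed examinations at other timepoints.

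**The narrow rule.** It appears in three places:
- Protocol Section 8.4.7: "A MAAE is an AE that leads to an unplanned visit to a healthcare practitioner".
- Protocol Section 10.3.3: "A MAAE is an AE that leads to a USV to a healthcare practitioner". On visits to the study site it adds: "This would include visits to a study site for unscheduled assessments not required per protocol".
- SAP Section 6.3.1: "MAAE which is defined as an AE that leads to an unscheduled visit to a healthcare practitioner".

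**Use of the endpoint.** MAAEs from Day 1 to end of study are a primary endpoint (Protocol Section 3, SAP Section 3.1). SAP Section 6.3.1.2 tabulates "All unsolicited medically attended AEs up to 28 days after injection and up to EoS throughout the study", and the treatment-related subset likewise.

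**Collection windows.** Protocol Section 8.4.1 collects SAEs from consent. It collects AESIs, MAAEs and AEs leading to withdrawal from study intervention to the end of participation. For everything else: "All other (unsolicited) AEs will be collected from the time of the administration of study vaccination through 28 days".

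**The concern.** A site that follows the footnote reports a clinically significant finding at a routine post-injection visit as an MAAE. A site that follows the definition does not, unless the finding also leads to an extra visit. Both sites are complying with the current text.

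Two things are at stake. First, the MAAE percentage in each arm depends partly on which sentence the site staff worked from. Second, the 28-day limit on other unsolicited AEs means that after Day 28 the difference is more than a label: it can decide whether the event reaches the database.

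**Working it through.** **1. The plan's own safety figures.** Protocol Section 9.3 gives the chance of seeing at least one participant with an AE, which is 1 − (1 − p)^n:

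| n | p | Computed | Stated |
|---|---|---|---|
| 60 | 5% | 1 − 0.95^60 = 95.4% | about 95% |
| 60 | 3% | 1 − 0.97^60 = 83.9% | about 84% |
| 30 | 9.5% | 1 − 0.905^30 = 95.0% | about 95% |
| 30 | 7.5% | 1 − 0.925^30 = 90.4% | about 90% |

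All four reproduce. The point below concerns definitions and does not depend on them. They do show that the arms are sized around seeing a first event, so one reclassified participant is visible.

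**2. Where the two rules agree and differ.**

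| Finding | Footnote d | Sections 8.4.7 and 10.3.3, SAP 6.3.1 |
|---|---|---|
| At an unscheduled visit, after injection | MAAE | MAAE |
| At a scheduled visit, after injection, and it leads to an extra visit | MAAE | MAAE |
| At a scheduled visit, after injection, no extra visit | MAAE | Not an MAAE |
| Before injection | MAAE on the literal text | Outside MAAE collection |

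The conflict that reaches the endpoint is the third row. Such findings can arise: symptom-directed examinations are allowed at later visits, and vital signs are taken at least 30 minutes after injection on Day 1.

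The fourth row is dealt with elsewhere. Protocol Section 8.4.1 sends non-serious pre-injection occurrences to medical history. Protocol Section 8.3 starts MAAE collection after dosing. The SAP Section 6.1 analysis period for MAAEs starts at injection. SAP Section 6.3.1 keeps only events that are new or worsened after vaccination.

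**3. Before and after the 28-day limit.** Through Day 28 a third-row finding that is an AE is collected as an unsolicited AE under either rule, so only the MAAE classification changes. After Day 28, Section 8.4.1 leaves a new event four routes into the data: SAE, AESI, AE leading to withdrawal, or MAAE. A new non-serious finding that is not an AESI and does not lead to withdrawal is therefore recorded under footnote d and not under the definition. The schedule has clinic visits in columns beyond those marked for unsolicited AEs, including the last visit, so the situation can occur. The visit days are redacted.

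**4. Whether the documents settle it.** SAP Section 1 says that the SAP prevails where methods differ. The SAP carries the narrow text in Section 6.3.1 and the broad text in Appendix E, so that clause does not choose between them. SAP Section 7 lists the changes from the protocol and does not mention MAAEs.

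**5. Size.** Arm sizes are 60 and 30 (Protocol Table 4). One more participant with an MAAE adds 1/60 = 1.7 points or 1/30 = 3.3 points.

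The documents give neither an MAAE rate nor a frequency of scheduled-visit findings. As an illustration only, assume that a share b of participants, 5% to 15%, has an MAAE under the narrow rule. Assume also that a share x, 2% to 10%, independently has a qualifying finding at a scheduled visit only. The broad-rule rate is b + (1 − b)x:
- b = 5%: 6.9% (x = 2%) to 14.5% (x = 10%).
- b = 15%: 16.7% (x = 2%) to 23.5% (x = 10%).

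That is about 1 to 6 more participants in a 60-person arm and about 0.5 to 3 in a 30-person arm.

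**The case against.** The strongest reply is that the overlap is narrow. Footnote d sits on a row marked only at Screening and Day 1, and the Day 1 arm and lymph-node check comes before injection. Later examinations are discretionary, and participants are healthy adults aged 18 to 49. SAP Section 6.3.1 states one definition in its analysis text and has the investigator judge AEs for MAAE status. Appendix E merely reproduces the protocol schedule. No hypothesis is tested. Assignment is central and randomized, and assessors are blinded.

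Most of this stands, and it limits the point. The ambiguity lies in what sites report; a reader might infer that the SAP has a second tabulation rule, but it does not. Site differences would add noise or shift the level in all arms. Randomization is not stratified, so chance imbalance is possible in small arms, but no systematic difference is to be expected.

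Three stronger readings are tempting and are not supported:
- **Pre-dose findings inflate the endpoint.** The footnote's literal text reaches them, but the provisions in step 2 of the working keep them out of the MAAE tables. What remains is an untidy instruction to sites.
- **The endpoint stops measuring care-seeking.** Neither document says that it measures this. The definition itself already counts unscheduled visits to the study site.
- **Two such findings in a 30-person arm add 6.7 points.** Participants are counted once, so 2/30 applies only if the findings fall in two different participants, neither with another MAAE.

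The reply does not remove the third row of the table or the consequence after Day 28.

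**Conclusion.** The inconsistency is real and stands in the current text of both documents. It is confined to post-injection findings at scheduled visits that lead to no unplanned visit. For these, two sites can each follow the text and report a primary endpoint differently. After Day 28 the reading also decides whether a new non-serious finding that is not an AESI and does not cause withdrawal is recorded at all.

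The size is known only per participant: 3.3 points in a 30-person arm and 1.7 points in a 60-person arm for each additional participant with an MAAE. The ranges in the working rest on assumed rates and on independence, and the conclusion does not need them. Error rates and power are unaffected because the study is descriptive. The damage is to the consistency and meaning of the MAAE percentages. The correction is inexpensive and worth making.

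**What to change.** Reconcile the passages to one MAAE rule, used for both collection and analysis. There are two coherent routes.

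**(a) Keep the narrow definition.** Amend footnote d in the protocol schedule and in SAP Appendix E. A clinically significant post-injection finding is then assessed as an AE within the Section 8.4.1 collection periods, and reported as an MAAE only if it meets Section 10.3.3. Leave pre-injection events to Section 8.4.1, where non-serious occurrences go to medical history and SAEs are collected from consent. The cost is one footnote in each document and a clarification to sites. The price is that new non-serious scheduled-visit findings after Day 28, other than AESIs and those leading to withdrawal, are no longer captured.

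**(b) Keep the wider capture, if that is what the footnote intends.** Amend Protocol Sections 8.4.7 and 10.3.3 and SAP Section 6.3.1 to include post-injection findings at scheduled visits. Flag those events in the data, and tabulate MAAEs with and without them. The cost is three definitions, one flag, an additional tabulation and the same site clarification.

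If data have already been collected under mixed readings, tabulating scheduled-visit findings separately would still make the reported MAAE percentages interpretable. It cannot recover findings after Day 28 that a site, following the definition, never recorded.
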